Subjects may or may not benefit from improvement in lichen sclerosus. All subjects in the study are expected to have some benefit from the treatment procedures. Subject will receive treatment procedures at no cost. This study will benefit the advancement of medicine by generating data on safety and efficacy that will aid in the development of an alternative treatment options to ultra-potent topical corticosteroids (such as clobetasol propionate). This study will benefit the advancement of medicine by generating data on safety and efficacy that will aid in the development of an alternative or adjunctive treatment option for female patients who do not improve with topical corticosteroid use for vulvar lichen sclerosus.

 Candela Corporation Confidential	Clinical Study of the CO₂RE Laser Device for Treatment of Vulvar Lichen Sclerosus				
	Protocol #	DHF25211	Rev. Date	February 19, 2019	Page 21 of 39

Payment for Participation

Subjects will be paid a total of up to \$200 for up to 10 study visits (\$20 per visit) for all study visits and evaluations. Subjects will not pay for office visits, examinations or procedures that are part of this clinical study. Subjects who do not complete all study-related procedures and requirements will receive partial payments according to the treatment and follow-up visits that were completed (\$20 per visit). Subjects who are biopsied at baseline, at the 6-week follow-up and the 6-month follow-up will receive an additional \$200 (~\$67 per visit). Payments will be issued upon study completion.

ETHICS AND GOOD CLINICAL PRACTICE

This study will be carried out in compliance with the following:

- Syneron Candela's Standard Operating Procedures (SOPs).
- Declaration of Helsinki (current version).
- US Code of Federal Regulations (Title 21CFR including parts 50, 56 and 812 governing informed consent and IRB regulations).
- International Conference on Harmonization (ICH) Harmonized Tripartite Guideline for Good Clinical Practice (GCP), 1996.

QUALITY ASSURANCE AND STUDY MONITORING

Study Monitoring/Auditing/Inspection

The Study Monitor will be responsible for monitoring the study sites to review the data being collected. The sponsor shall implement and maintain quality control and quality assurance procedures with written standard operating procedures (SOPs) to ensure that the trial is being conducted and data are generated, documented and reported in compliance with the protocol, Good Clinical Practice (GCP) and applicable regulatory requirements. Visits will be made prior to the initiation of the study, at scheduled intervals throughout the study, and at termination of the study.

Once enrollment and treatments have begun, monitoring visits will take place more frequently pending enrollment and study activities.

The sponsor and site will maintain regular phone and e-mail correspondence throughout the study to confirm compliance of study procedures.

The investigator/institution agrees to allow the study monitor and other authorized personnel direct access to source data/documents for trial related monitoring, the clinical supplies

 Candela Corporation Confidential	Clinical Study of the CO₂RE Laser Device for Treatment of Vulvar Lichen Sclerosus				
	Protocol #	DHF25211	Rev. Date	February 19, 2019	Page 22 of 39

storage/dispensing area and to provide all documents in the Investigator Regulatory Binder for review, and to assist site auditors in their activities if requested. Requests by the United States Food and Drug Administration (FDA) or regulatory agencies of other countries to inspect the study site may be made after adequate notification. The investigator may be required to assist the regulatory inspectors in their duties, if requested.

ADMINISTRATIVE PROCEDURES

Supply and Disposition of Study Devices

The CO₂RE Intima disposable external handpieces will be supplied to the participating clinics. Unused equipment will be returned to the sponsor at the end of the study.

Control & Disposition of the Investigational Device

The CO₂RE system will be used according to the instructions of the Sponsor, Candela Corporation, and the manufacturer, Syneron Medical Ltd. At the end of this study, any materials provided specifically for use in this study must be returned to the Sponsor, as described in the Clinical Trial Agreement and study budget.

Informed Consent

The Study Personnel will obtain written Informed Consent prior to the subject's participation in any study procedures. The Study Personnel will inform the subjects of the experimental procedure to be utilized and assure the subjects that their decision regarding participation in the study will have no bearing on the quality of medical care received and that their decision whether to participate in the study is strictly voluntary.

During the initial interview, the subject will be assured that they are free to change their mind and will be allowed to participate in the study or withdraw from the study with no adverse effect on their standard medical care.

Monitoring Plan

At least 3 monitoring visits are projected during the whole study. The frequency of which will be based on enrollment, study activities and the study visit scheduled. The first visit is scheduled at the initiation of the study prior to the first subject treatment in the study. The second visit is scheduled after enrollment and treatment has been initiated and a third visit will be for a close-out visit for the study. Interim visits may be conducted as needed to assure compliance to the study protocol and regulatory requirements. The number and frequency of monitoring visits may also be increased per the sponsor decision to collect data and images post treatment.

Case Report Forms

Paper case report forms will be used in this trial. All protocol-required information collected during the study must be entered in the appropriate field of the case report form (CRF). The investigator, or designated representative, should complete the appropriate CRF fields as soon as possible after information is collected. The information must match the information that exists as source documents in the clinic chart, hospital chart, and/or investigator's files. An explanation should be given for all missing data.

It is the investigator's responsibility to assure the accurate completion, review, and approval of all CRFs and the timely completion and submission of all adverse event forms.

Record Maintenance

The investigator shall retain a copy of all study documents in accordance with FDA regulations which specify that records should be kept for a period of two years: 1) following the date a marketing application either is approved or disapproved for use, or 2) following notification to the FDA that no application is being filed and/or that the study has been discontinued.

If an investigator leaves the study site before record retention obligations have expired, the sponsor should be notified in writing of the person designated to retain the study documents during and after the study.

Handling of clinical data. The data are entered into a secure database to which only the Sponsor has access. Admission to the database should require access to a password-protected network secured by the Sponsor. This database is maintained by Syneron Corporation who performs backups, data verification, and application upgrades. All equipment housing the clinical data should be located in locked rooms or a secure computer network. The only individuals, who view, extract and analyze data for protocol reports and publications are physicians and nurses who are members of the study team or sponsors. Only authorized personnel of the sponsors will have access to databases.

Any paper copies of subject medical records or research records should be stored in secure cabinets at the study site.

PUBLICATION POLICY

The investigator will not publish the study results and will not disclose confidential information received from Candela Corporation without prior written agreement from Syneron. Such confidential information shall include any and all information relating to this study as described in the Clinical Trial Agreement. In the event that Candela Corporation consents to the publication of data from this study, the investigator will provide Candela Corporation manuscripts for review sixty (60) days before submission for publication. Candela Corporation

will have no editorial rights over manuscripts. The investigator will also provide Candela Corporation with advance notice of at least sixty (60) days, of any presentation, lecture, abstract session, etc., in which any results from the study will be disclosed.

REFERENCES

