Secondary Objectives	
 • Evaluate sexual function at the 3-month and 6-month follow-ups compared to baseline. • Evaluate histological markers at the 6-week and 6-month follow-ups compared to baseline. • Evaluate discomfort following each treatment. • Evaluate the safety of CO₂RE treatments for VLS during the study. • Evaluate subject satisfaction at the 6-week, 3-month, 6-month and 12-month follow-up visits. 			

Primary Endpoint	Change from baseline in presence and severity of symptoms (5-point severity scale), clinical signs (3-point severity scale) and architectural changes (3-point severity scale) at the 6-week, 3-month, 6-month and 12-month follow-up visits. (Appendices I & II).
Secondary Efficacy Endpoints	
The following parameters will be measured during the study:
 
 Sexual function, using the Female Sexual Function Index (Appendix III), at baseline and at the 3-month and 6-month follow-ups. Histological signs (degree of hyperkeratosis, epidermal atrophy and dermal inflammation) at baseline and at 6 weeks and 6 months after the final treatment. Subject satisfaction, using a 5-point Likert scale (-2=very dissatisfied; 2=Very satisfied), will be assessed at the 6-week, 3-month and 6-month follow-up visits.
Safety Endpoints	
Evaluate the safety of the CO₂RE device for the treatment of VLS in female subjects:
 
 Pain/discomfort level using a 10-point Numerical Scale Response (NSR) after each treatment. Number, severity and type of adverse events recorded throughout course of the study. 1 week ± 2 days post first treatment safety phone call to review 1-week patient diary.

INTRODUCTION AND RATIONALE

Background

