Change from baseline in presence and severity of symptoms (5-point severity scale), clinical signs (3-point severity scale) and architectural changes (3-point severity scale) at the 6-week, 3-month, 6-month and 12-month follow-up visits. (**Appendices I & II**).

Secondary Safety Endpoints

Evaluate the safety of the treatment:

1. Clinical evaluation of treated area at each study visit. Clinical photography will be performed for study documentation (**Appendix IV**).
2. Pain/discomfort level using a 10-point Numerical Scale Response (NSR) after each treatment (**Appendix V**).
3. Number, severity and type of adverse events recorded throughout course of the study.
4. 1 week ± 2 days post first treatment safety phone call (review of 1-week patient diary) – (**Appendix VI**).

Secondary Efficacy Endpoints

1. Sexual function, using the Female Sexual Function Index (**Appendix III**), at baseline and at the 3-month and 6-month follow-ups. *An overall score ≤ 26.55 is classified as Female Sexual Disorder (FSD).*¹⁵
2. Histological signs (degree of hyperkeratosis, epidermal atrophy and dermal inflammation) at baseline and at 6 weeks and 6 months after the final treatment.
3. Subject satisfaction, using a 5-point Likert scale (-2=very dissatisfied; 2=Very satisfied), will be assessed at the 6-week, 3-month, 6-month and 12-month follow-up visits (**Appendix VII**).

SUBJECT POPULATION

Up to 45 female subjects who meet the following inclusion / exclusion criteria may be enrolled.

Subject Withdrawal and Replacement

Subjects enrolled in the study can discontinue their participation at any time for any reason without prejudice or reduction in the quality of their medical care. The investigator or sponsor can terminate a subject's participation in this study to protect the subject's health or if the subject fails to follow directions resulting in noncompliance to study procedures. Subjects who withdraw or are terminated from the study may be replaced to allow up to 45 subjects to complete the study. Subjects who fail to complete the treatment will be replaced and will not be evaluable.

Inclusion Criteria

1. Able to read, understand and sign informed consent for study participation;
2. Female subjects with age 18-80 years;
3. Biopsy demonstrates biopsy-proven lichen sclerosus and/or there are characteristic changes for vulvar lichen sclerosus on physical examination;

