Table 2. Study Measurements

Assessment	When to conduct	Method
Complete the Inform Consent form and Eligibility Screening and Medical History	During the screening visit / prior to the 1 st treatment	Physician or staff will complete the form with the study subject
PAP smear if not up-to-date (within 3 years according to ACOG guidelines)		Patient should provide lab results of up-to-date normal cell cytology
Urine pregnancy test for women capable of becoming pregnant		Patient should have a negative pregnancy test
Gynecological exam		Physician will examine the vulvar and vaginal area for any signs of active infection or atypical nevi
Vulvar biopsy of treatment area (optional)	Prior to the 1 st treatment and at the 6-week and 6-month follow-ups	Biopsies will be obtained from up to 10 subjects to conduct histological assessment. Lab reports will be provided to show changes in markers compared to baseline.
Subject assessment of symptoms	
 • Baseline or pre-Tx. 1 • At the 6-week, 3-month, 6-month and 12-month follow-up visits 	Subjects will complete the Symptom Severity Questionnaire, according to the pre-defined scales (Appendix I)
Physician assessment	
 • Baseline or pre-Tx. 1 • Prior to treatments • At the 6-week, 3-month, 6-month and 12-month follow-up visits 	Physician will assess clinical signs associated with VLS, according to the pre-defined scales (Appendix II)
Subject assessment of sexual function	
 • Baseline or pre-Tx. 1 • At the 3-month and 6-month follow-up visits 	Subjects will complete the Female Sexual Function Index (FSFI) – Appendix III
Clinical evaluation and photographs of treated area	
 • Baseline or pre-Tx. 1 • Prior to treatments • At the 6-week, 3-month, 6-month and 12-month follow-up visits 	Physician will evaluate the treatment area. Physician or staff will take photographs of the treatment area (Appendix IV)
Treatment pain assessment	Immediately after each treatment	NSR Scale (Appendix V)
Subject 1-week daily diary - reviewed at the 1wk FU after the first treatment	The daily diary will be provided at the 1 st treatment visit and reviewed by phone during the 1-week safety evaluation	Subjects will be requested to complete a daily diary with data regarding their comfort, AE, and activity (7 days of follow-up post 1st treatment) – Appendix VI

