Following the first treatment:

1. Subjects will receive a daily diary, which they will be requested to complete, regarding their comfort and any adverse events for the 7-day period following treatment.

Following each treatment session

1. If the subject experiences itch or discomfort after treatment, ice packs may be applied to the treatment area.
2. Temporary erythema (redness) and edema (swelling), as well as heat and tightening sensations, may occur up to a few hours after the treatment. If the subject feels significant discomfort longer than a few hours, an over-the-counter pain medication such as Tylenol® (Acetaminophen) may be used. Nonsteroidal anti-inflammatory drugs (NSAID), such as aspirin, Ibuprofen (Advil, Motrin), naproxen (Aleve, Anaprox, Naprelan, Naprosyn), etc. should be avoided unless the patient does not experience symptomatic relief with or is contraindicated to acetaminophen.
3. On the evening after the treatment, subjects should wash the treated areas gently with lukewarm water and avoid very hot or cold water in these areas. Generally, subjects may use their regular cleanser after treatment, as long as these are not mechanical scrubs or exfoliants.
4. Subject should refrain from sexual activities for a period of 7 days.
5. Any pain, fever or unusual discharge should be immediately reported.

 Candela Corporation Confidential	Clinical Study of the CO₂RE Laser Device for Treatment of Vulvar Lichen Sclerosus				
	Protocol #	DHF25211	Rev. Date	February 19, 2019	Page 16 of 39

Follow-up Visits

1. All subjects will be requested to return to the clinic at the following time-points during the study to assess the clinical safety and performance of the device:
 - 6 weeks post last treatment – 6wk FU ± 2 weeks.
 - 3 months post last treatment – 3m FU ± 2 weeks.
 - 6 months post last treatment – 6m FU ± 2 weeks.
 - 12 months post last treatment – 12m FU ± 2 weeks.
2. At the follow-up visits, the following assessments will be performed, and data recorded:
 - Review changes in medication, medical history and AE, if applicable, from last visit.
 - Photographs of treated area.
 - Optional biopsy of treated area (6-week and 6-month follow-up only).
 - Subject assessment of symptom severity.
 - Investigator assessment of clinical signs.
 - Subject Satisfaction.

DATA ANALYSIS

Recording

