APPENDIX VI – SUBJECT POST-TREATMENT DAILY DIARY QUESTIONNAIRE

At the 1st treatment study visit, subjects will be provided with a 1-week daily diary and instructed to rate the discomfort they experienced on the day of treatment and each day following treatment, according to the following scale:

	Score and Rate
	0 - No Discomfort
	1 - Mild Discomfort
	2 - Moderate Discomfort, but tolerable
	3 - Very Painful, barely tolerable

Additionally, subjects will be instructed to report any adverse (side) effects during the first week post-treatment and to describe the event on the questionnaire.

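### The 1-week safety call may come before the 7-day diary it is meant to review is finished, and the protocol states no later review or collection of that diary

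*Protocol*

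**What the plan says.** The call appears in the protocol's Table 1 (Study Synopsis, Safety Endpoints) as a "1 week ± 2 days post first treatment safety phone call to review 1-week patient diary". The same window is repeated under Secondary Safety Endpoints, item 4.

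The diary is described in three places:

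- Table 2 (Study Measurements) gives its length as "7 days of follow-up post 1st treatment" and says it is "reviewed by phone during the 1-week safety evaluation".
- The post-treatment instructions say that, after the first treatment, subjects complete it "regarding their comfort and any adverse events for the 7-day period following treatment".
- Appendix VI asks subjects to rate discomfort "on the day of treatment and each day following treatment" and to describe any side effects in that first week.

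The checklist under Prior to Each Treatment Procedure and the assessments listed under Follow-up Visits do not mention the diary.

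Adverse events are a separate safety endpoint covering the whole study. Under Table 2 they are collected by examination and interview before and immediately after the treatments, at every follow-up visit, and whenever a subject raises a concern.

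**The concern.** The purpose of the call is to go through a one-week diary, yet its lower limit falls before that week is over. A site can make the call on time and still review an unfinished record. Because the call is the only stated review, nothing in the text ensures that the remaining entries reach the study data. The call and its diary review are themselves a listed safety endpoint, so the window ought to allow that purpose to be met.

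A second, weaker issue is that daily solicitation follows treatment 1 alone. Treatment settings are chosen by the investigator within stated ranges and modes, so the first session need not represent later ones. For later sessions the protocol schedules no contact in the days after treatment. What is at stake is how complete and how even the record of mild, transient effects is across sessions.

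**Working it through.** This is date arithmetic; no power or error-rate calculation applies. Day 0 is the day of treatment 1.

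**Inputs**

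- Call: 1 week ± 2 days after treatment 1 (Table 1; Secondary Safety Endpoints).
- Diary: 7 days (Table 2; post-treatment instructions), with the treatment day rated as well (Appendix VI).
- Treatments: up to 5, at intervals of 4 ± 1 weeks (Table 1).
- First visit after the last treatment: 6 weeks ± 2 weeks (Study Duration and Timelines).
- Subjects: up to 45 (Table 1).

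**Call window.** 7 − 2 = day 5; 7 + 2 = day 9.

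**Diary days still to come after the call.** The text allows two readings of the last diary day: day 7 (diary on days 1 to 7) or day 6 (treatment day counted as the first of seven, so days 0 to 6). Days outstanding = last diary day − day of call, not below 0.

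| Call on day | Diary ends day 7 | Diary ends day 6 |
|---|---|---|
| 5 | 7 − 5 = 2 | 6 − 5 = 1 |
| 6 | 7 − 6 = 1 | 0 |
| 7, 8 or 9 | 0 | 0 |

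This counts the entry for the day of the call as already made, which is the lenient assumption.

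**Share of the window affected.** Two of five permitted days (2/5 = 40%) on the first reading, one of five (1/5 = 20%) on the second. These are shares of calls only if calls are spread evenly over the window, which is an assumption; the protocol does not say how calls will fall.

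**Diary coverage.** For a subject who has all five treatments, 7 of 5 × 7 = 35 post-treatment diary days, or 20%. If all 45 subjects had five treatments, 45 of 45 × 5 = 225 sessions, again 20%. Both 45 and five are maxima. The figure describes the diary, not adverse event collection.

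**Gap to the next scheduled adverse event interview after a later session**

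- After treatments 2 to 4 of a five-treatment course: 4 ± 1 weeks = 3 to 5 weeks (21 to 35 days).
- After the last treatment: 6 ± 2 weeks = 4 to 8 weeks (28 to 56 days).

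**The case against.** The strongest reply is that adverse event capture does not depend on the diary. Interview and examination are required around every treatment and at every follow-up visit, and subjects may report at any time. After each session they are told to report pain, a fever or abnormal discharge at once. An event on an unreviewed diary day would still be asked about before treatment 2. Pain is scored immediately after every treatment, which serves the objective on discomfort. The Case Report Forms section also requires missing data to be explained. The first-treatment-only diary is stated consistently throughout and contradicts nothing.

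Most of this stands. A reader might infer that post-treatment events are under-counted, or that an event rate per session would be biased downwards. The documents do not support either: other collection routes exist for every session, no per-session rate is defined, and no event rates are given from which a bias could be shown.

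The reply does not remove the timing mismatch, since the other routes do not complete or retrieve the diary. Nor do they match daily solicitation. The instruction to report at once names three complaints, whereas the anticipated effects also include bruising, blistering and burns. The pain score is taken immediately after the session and says nothing about the following days.

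**Conclusion.** The timing point holds and is minor. A compliant call on day 5 leaves one or two diary days unreviewed, depending on whether the diary ends on day 6 or day 7. A call on day 6 leaves one on the day-7 reading and none on the other. Calls on days 7 to 9 leave none. With no later review or collection stated, the daily solicited record can be incomplete, although the events themselves are still sought at later visits.

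The treatment 1 restriction is a design choice, not an error. Its consequence is uneven ascertainment: one week of daily solicited data after the first session, against scheduled interviews 3 to 5 weeks after later sessions and 4 to 8 weeks after the last, supplemented by spontaneous reports. Mild transient effects may be recorded less completely after later sessions; whether they will be, and by how much, cannot be computed from the protocol.

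**What to change.** 1. Reconcile the call window with the diary period wherever either appears (Table 1, Secondary Safety Endpoints, Table 2, post-treatment instructions, Appendix VI), so that the diary review cannot come before the last diary day. Say in the same edit whether the treatment day is the first of the seven diary days.
2. State that the completed diary is collected at the treatment 2 visit, and add this to the checklist for that visit. Any entry made after the call is then retrieved.
3. Optionally, give the same paper diary after each treatment and review it at the next visit already scheduled, with no added calls. If this is not done, present diary-based data as describing treatment 1 only.

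Items 1 and 2 cost a text edit and one checklist line. Item 3 costs copies of an existing form and some extra burden on subjects, which is a fair reason to decline it.
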